### **7.5.1.               Investigator Electrocardiogram Assessment**

A shift table of the investigators' assessment of ECG results at worst outcome during study compared with baseline values will be presented by dose cohort using the following categories: normal; abnormal, not clinically significant; abnormal, clinically significant; or missing. The number and percentage of subjects in each cross-classification group of the shift table will be presented. Subjects with a missing value at baseline or postbaseline will not be included in the denominator for percentage calculation. No formal statistical testing is planned.

A by-subject listing for ECG assessment results will be provided by subject ID number and visit in chronological order.

### **7.5.2.               Corrected QT Intervals**

The QT interval (measured in millisecond [msec]) is a measure of the time between the start of the Q wave and the end of the T wave in the heart's electrical cycle. The QT interval represents electrical depolarization and repolarization of the ventricles. The QT interval is affected by heart rate, and a number of methods have been proposed to correct QT for heart rate.

Corrected QT (QTc) intervals will be derived using Fridericia's correction (QTcF) as follows:

$$QTcF = \frac{QT}{\sqrt[3]{RR}}$$

where QT is measured in msec; RR = 60/Heart Rate (beats per min [bpm]) and RR is measured in seconds

QTcF will be listed by-subject.

## **7.6. Other Safety Measures**

No additional safety measures are specified in the protocol.

### **7.6.1. Post Treatment Anti-cancer Therapies**

All post treatment anti-cancer therapies will be provided in a by-subject listing sorted by subject ID number and administration date in chronological order.

## **7.7. Echocardiogram**

A by-subject listing will be provided for echocardiogram and multigated acquisition (MUGA) scan results by subject ID number and visit/time point in chronological order.

## **7.8. Changes From Protocol-Specified Safety Analyses**

There are no deviations from the protocol-specified safety analyses.

## **8. PHARMACOKINETIC (PK) ANALYSES**

### **8.1. PK Sample Collection**

Blood samples will be collected to measure concentrations and to estimate PK parameters of GS-1423 at protocol specified time points.

### **8.2. Statistical Analysis Methods**

#### **8.2.1. GS-1423 Plasma Concentration**

Plasma concentration for GS-1423 will be summarized using descriptive statistics (n, arithmetic mean, StD, coefficient of variation [%CV], median, min, max, Q1, Q3, geometric mean and 95% CI) for subjects in the PK Analysis Set by sampling time point and visit. Subjects in different dose cohorts will be presented separately. The sample size for each time point will be based on the number of subjects with nonmissing concentration data at that time point. The number of subjects with concentration BLQ will be presented for each time point. For summary statistics, BLQ values will be treated as 0.

The following table will be provided by dose level:

- Individual subject concentration data and summary statistics

The following figures may be provided by dose level:

- Mean ( $\pm$  StD) concentration data versus time (on linear and semilogarithmic scales)
- Median (Q1, Q3) concentration data versus time (on linear and semilogarithmic scales)

GS-1423 plasma concentration data and PK sampling details will be listed for all subjects in the PK Analysis Set. Mean and median postdose concentration values that are  $\leq$  LOQ, if any, will not be displayed in the figures and remaining points connected.

#### **8.2.2. GS-1423 PK Parameters**

For subjects in Phase 1a Part A, relevant PK parameters will be estimated using Phoenix WinNonlin® software and utilizing standard noncompartmental methods. The linear up log down rule will be applied in conjunction with the appropriate noncompartmental model, with input values for dose level, dosing time, plasma concentration, and corresponding real time values, based on drug dosing times whenever possible. Descriptive statistics will be presented for PK parameters of GS-1423 by dose level/cohort.

All predose sample times before time-zero will be converted to 0. For area under the curve (AUC), samples BLQ of the bioanalytical assays occurring prior to the achievement of the first quantifiable concentration will be assigned a concentration value of 0 to prevent overestimation of the initial AUC. Samples that are BLQ at all other time points will be treated as missing data in WinNonlin. The nominal time point for a key event or dosing interval ( $\tau$ ) may be used to

permit direct calculation of AUC over specific time intervals. The appropriateness of this approach will be assessed by the PK scientist on a profile by profile basis.

Pharmacokinetic parameters such as  $\lambda_z$  and  $t_{1/2}$  are dependent on an accurate estimation of the terminal elimination phase of drug. The appropriateness of calculating these parameters will be evaluated upon inspection of PK data on a profile-by-profile basis by the PK scientist.

The PK parameters for GS-1423 presented in [Table 2](#) will be computed for all subjects in the PK Analysis Set using profiles from Cycle 1 [predose through Cycle 2 predose (Cycle 1 Day 15)] and Cycle 4 [predose through Cycle 5 predose (Cycle 4 Day 15)], as applicable.

**Table 2. PK Parameters for GS-1423**

Analyte	Parameters
GS-1423	AUC tau , C max , C trough , T max , CL ss , V ss , C last , T last , AUC last , AUC tau /Dose, C max /Dose, and C trough /Dose, if applicable

Individual subject PK parameter data will be listed and summarized using descriptive statistics (n, arithmetic mean, StD, coefficient of variation [%CV], median, min, max, Q1, Q3, geometric mean, 95% CI, mean and StD of the natural log-transformed values) for all subjects for whom PK parameter(s) can be derived. The sample size for each PK parameter will be based on the number of subjects with nonmissing data for that PK parameter.

The following table will be provided by dose level:

- Individual subject plasma PK parameters and summary statistics will be presented for PK parameters of GS-1423 by dose cohort.

Individual data on determination of half life and corresponding intra-subject correlation coefficient will be listed.

## **9. IMMUNOGENICITY ANALYSES**

### **9.1. ADA Sample Collection**

Plasma samples will be collected to measure anti-drug antibody (ADA) against GS-1423 at protocol specified time points.

### **9.2. Statistical Analyses Methods**

Immunogenicity data will be summarized for all subjects by different dose cohorts and across dose cohorts in the Immunogenicity Analysis Set. Immunogenicity of GS-1423 will be evaluated based upon the incident of ADA. The number and proportion of subjects exhibiting positive ADA status, defined as ADA presence in plasma confirmed in validated assay and reported by bioanalytical laboratory, will be summarized at each specified time point. The number and proportion of subjects exhibiting positive ADA status at any post-baseline time point will also be summarized.

A by-subject listing for ADA status at each time point, along with treatment, nominal sampling day, actual date and time of sampling, and reason of sample not collected and titer for subjects with positive ADA status will be provided by subject ID number and time point in chronological order.

CC1

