6.6.2.1. Immunogenicity Assessment in Phase 1a Cohorts

Table 6-8. Schedule of ADA Assessments for QW

| | |
|--|----------------|
| Cycle 1 Day 1 | Predose |
| Cycle 3 Day 1 | Predose |
| Cycle 4 Day 1 | Predose |
| Cycle 6 Day 1 | Predose |
| Cycle 6 Day 8 | 168 h postdose |
| At Cycle 8 Day 1 and subsequent every 12 cycles | Predose |
| 30-Day Follow-up Visit (30 days after last dose) | X |
| Posttreatment Follow-up Visit (3 months after last dose) | X |

ADA anti drug antibody against GS 1423; h hour(s); QW every week

Note: Blood will be drawn at Cycle 6, Day 8 (\pm 4 hours) even if the subject discontinues treatment at Cycle 7.

Table 6-9. Schedule of ADA Assessments for Q2W

| | |
|--|----------------|
| Cycle 1 Day 1 | Predose |
| Cycle 2 Day 1 | Predose |
| Cycle 3 Day 1 | Predose |
| Cycle 4 Day 1 | Predose |
| Cycle 4 Day 15 | 336 h postdose |
| At Cycle 6 Day 1 and subsequent every 6 cycles | Predose |
| 30-Day Follow-up Visit (30 days after last dose) | X |
| Posttreatment Follow-up Visit (3 months after last dose) | X |

ADA anti drug antibody against GS 1423; Q2W every 2 weeks

Note: Blood will be drawn at Cycle 4, Day 15 (\pm 1 day) even if the subject discontinues treatment at Cycle 5.

[figure not shown]
Table 6-10. Schedule of ADA Assessments for Q3W

| | |
|--|----------------|
| Cycle 1 Day 1 | Predose |
| Cycle 2 Day 1 | Predose |
| Cycle 3 Day 1 | Predose |
| Cycle 3 Day 22 | 504 h postdose |
| Cycle 6 Day 1 | Predose |
| At Cycle 8 Day 1 and subsequent every 4 cycles | Predose |
| 30-Day Follow-up Visit (30 days after last dose) | X |
| Posttreatment Follow-up Visit (3 months after last dose) | X |

ADA = anti drug antibody against GS 1423; Q3W = every 3 weeks

Note: Blood will be drawn at Cycle 3, Day 22 (\pm 1 day) even if the subject discontinues treatment at Cycle 4.

CCI

CCI

CCI

CCI

The document page is heavily redacted. A large black rectangular redaction box covers the top half of the page. Below this, there are several smaller redaction boxes: one on the left side, one spanning the middle section, and two on the right side. The redaction boxes are solid black and completely obscure the underlying text.

CCI

CCI

CCI

CCI

CCI

CCI

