8.1.3. Secondary Endpoints

The secondary endpoints of this study are:

Phase 1a Part A

- Percentage of subjects with treatment-emergent AEs
- Percentage of subjects with treatment-emergent Grade 3 or 4 laboratory abnormalities
- Percentage of subjects with clinically significant abnormal 12-lead ECG
- GS-1423 PK parameters (AUC_{tau})
- Percentage of subjects who developed ADA

[figure not shown]
Phase 1a Part B

- GS-1423 PK parameters (AUC_{tau})
- Percentage of subjects who developed ADA

[figure not shown]
Phase 1b Cohort 1

- Percentage of subjects with treatment-emergent AEs
- Percentage of subjects with treatment-emergent Grade 3 or 4 laboratory abnormalities
- Percentage of subjects with clinically significant abnormal 12-lead ECG

CCI

CCI

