8.9. Immunogenicity Analysis

Immunogenicity to GS-1423 will be evaluated based upon the incidence of ADA formation. Number and percentage of positive or negative ADA results at each specified time point will be summarized by dose level/cohort using the Immunogenicity Analysis Set. Supporting data including treatment, nominal sampling day, actual date and time of sampling, and ADA results, will be included in a listing.

CCI [REDACTED]

[REDACTED]

[REDACTED]

[REDACTED]

CCI [REDACTED]

[REDACTED]

[REDACTED]

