### **3.1.6. Immunogenicity Analysis Set**

The Immunogenicity Analysis Set will include all subjects in the Safety Analysis Set who have at least 1 nonmissing postdose antidrug antibody (ADA) status reported. This is the primary analysis set for all immunogenicity analyses.

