### **3.8.3. Selection of Data in the Event of Multiple Records in an Analysis Visit Window**

Depending on the statistical analysis method, single values may be required for each analysis window. For example, change from baseline by visit usually requires a single value, whereas a time-to-event analysis would not require 1 value per analysis window.

If multiple valid, nonmissing measurements exist in an analysis window, records will be chosen based on the following rules if a single value is needed:

- For baseline, the last nonmissing value on or prior to first dosing date of study drug will be selected, unless specified differently. If there are multiple records with the same time or no time recorded on the same day, the baseline value will be the average of the measurements for continuous data, or the measurement with the lowest severity (eg, normal will be selected over abnormal for safety electrocardiogram [ECG] findings) for categorical data.

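### SAP 9.2 counts any post-baseline ADA positive without using the subject's baseline, so if some subjects are ADA-positive before dosing the planned summaries may not give the percentage who developed ADA

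*SAP*

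**What the plan says.** Protocol 8.1.3 lists "Percentage of subjects who developed ADA" as a secondary endpoint for Phase 1a Part A. Protocol 8.9 adds: "Immunogenicity to GS-1423 will be evaluated based upon the incidence of ADA formation". It does not say what counts as formation, and the only summary it plans is of positive and negative results by time point.

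SAP 9.2 defines a positive status as ADA found in a plasma sample by the validated assay. It plans two kinds of summary, by cohort and across cohorts. The first is positives, which "will be summarized at each specified time point". The second is: "The number and proportion of subjects exhibiting positive ADA status at any post-baseline time point will also be summarized". It also plans "A by-subject listing for ADA status at each time point", with titer for positive subjects.

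SAP 3.1.6 admits to the Immunogenicity Analysis Set subjects "who have at least 1 nonmissing postdose antidrug antibody (ADA) status reported". It asks for no baseline result. Table 6-9 in Protocol 6.6.2.1, "Schedule of ADA Assessments for Q2W", does schedule a predose sample at Cycle 1 Day 1, and SAP 3.8.3 has a general baseline rule: "For baseline, the last nonmissing value on or prior to first dosing date of study drug will be selected, unless specified differently".

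The blacked-out block after SAP 9.2 sits where Section 10 falls in the contents list. Nothing here depends on it.

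**The concern.** To develop ADA is to go from not having it to having it. The any-post-baseline line records only that ADA was present at some time after dosing. It is the one subject-level percentage in the plan, so a reader will take it as the endpoint. For a subject who was positive before the first dose and stays positive, it reports an event that did not happen on treatment.

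Elsewhere the SAP does tie an outcome to its starting point. A treatment-emergent laboratory abnormality in SAP 7.2.2.1 must worsen from baseline, and a rule covers a missing baseline. ADA has no such derivation, although its endpoint is worded as a change.

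At stake is the summarized rate of a secondary endpoint. Part A cohorts are so small that one subject visibly moves it.

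**Working it through.** **Inputs**
- Samples (Protocol Table 6-9, Q2W): predose on Day 1 of Cycles 1, 2, 3 and 4, then Cycle 4 Day 15, then later cycles and follow-up.
- Cohort size (SAP Table 1): 3 to 6 in Cohorts 3 to 7; 1, or 3 to 6, in Cohorts 1 and 2.
- Planned maximum for Part A (SAP 1.3): 53. This reproduces: 42/0.9 = 46.7, rounded up to 47, plus 6 = 53.
- Share of subjects ADA-positive at baseline, b: not in the documents. Assumed 0 to 10% for illustration.

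The plan states no ADA figure, so there is none to reproduce.

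**Step 1. Effect of one subject.** Let N be the subjects analysed, P those positive at any post-baseline time, and K those of the P who were already positive at baseline and show no boost.
- Planned line: P/N.
- Newly positive, over all subjects: (P − K)/N.
- Difference: K/N, that is 100/N percentage points per affected subject: 33.3 at N=3, 16.7 at N=6, 1.9 at N=53.
- If K = 0 the difference is zero.

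**Step 2. What the planned lines can recover.** Assume complete baselines. The Cycle 1 Day 1 row gives B0, the number positive at baseline, and the any-post-baseline line gives P. Neither gives K, which can lie anywhere from max(0, B0 + P − N) to min(B0, P). The number of developers, P − K, therefore lies between max(0, P − B0) and min(P, N − B0).

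| N | B0 | P | Developers |
|---|---|---|---|
| 6 | 0 | 1 | exactly 1 |
| any | any | 0 | exactly 0 |
| 1 | 1 | 0 or 1 | exactly 0 |
| 6 | 1 | 6 | exactly 5 |
| 6 | 1 | 1 | 0 to 1 |
| 6 | 1 | 2 | 1 to 2 |
| 6 | 2 | 4 | 2 to 4 |

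**Step 3. Same planned output, different endpoint (N=6).** Take the first five samples, with every other result negative.
- Cohort A: one subject is positive at all five samples.
- Cohort B: one subject is positive only at Cycle 1 Day 1; another is positive at the four later samples.

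Both cohorts give time-point rows of 1, 1, 1, 1, 1 and an any-post-baseline line of 1/6 (16.7%). Developers number 0 in A and 1 in B. No planned summary separates them.

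**Step 4. How often it could matter.** The chance of at least one baseline-positive subject is 1 − (1 − b)^N.

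| Assumed b | N=6 | N=53 |
|---|---|---|
| 0% | 0% | 0% |
| 2% | 11.4% | 65.7% |
| 5% | 26.5% | 93.4% |
| 10% | 46.9% | 99.6% |

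A baseline-positive subject is necessary for the excess but not sufficient. If a share s of them is positive again without a boost, the expected excess is b × s: from 0 (s=0) to 5.0 points (s=100%) at b=5%, and from 0 to 10.0 points at b=10%. The high chances at N=53 go with only 1.9 points per affected subject, and 53 is an enrolment ceiling that includes a non-evaluable allowance and 6 optional subjects.

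**The case against.** The best reply is that nothing is lost. Baseline positives appear in the Cycle 1 Day 1 row. The listing shows every subject's status at every time point, and with cohorts this small a reader can classify each subject by eye. The endpoint is secondary and descriptive, and SAP Section 1 says the study stopped after Part A and will have a synoptic report. Protocol 8.9 itself left formation undefined and planned only time-point counts, so the SAP follows it and adds a subject-level line.

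All of that is true, and it sets the severity. It does not correct the summarized percentage. Deriving the endpoint from a listing without a written rule leaves baseline positives, missing baselines and the denominator to be settled after the results are seen.

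Three stronger readings are tempting, and the documents do not support them.
- A reader might infer that any baseline-positive subject makes the planned lines fail. Step 2 shows cases with baseline positives where the number of developers is still exact.
- A reader might infer that the rate must be taken among baseline-negative subjects. The endpoint speaks of subjects, and SAP 9.2 summarizes the whole Immunogenicity Analysis Set; a baseline-negative denominator is an option, not something the plan got wrong.
- A reader might count a subject who is positive, then negative, then positive again as plainly not a developer. The documents do not settle that case, so the example in Step 3 avoids it.

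**Conclusion.** The point holds in conditional form. If some subjects are ADA-positive before the first dose, the summaries in SAP 9.2 may not give the percentage who developed ADA, because no planned line links a later result to the same subject's baseline. The any-post-baseline line then exceeds the newly positive percentage of all subjects by 100/N points for each baseline-positive subject who is positive again without a boost. With complete baselines and no baseline positives, it equals the endpoint.

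This rests on reading *developed* as negative at baseline and positive later, which fits the wording but is not defined in either document. The actual size cannot be stated, because no baseline rate is given. Severity is minor: what is missing is a derivation rule, not data.

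**What to change.** In SAP 9.2:
- Define developed ADA as ADA-negative at baseline, with baseline taken by the SAP 3.8.3 rule, and at least one positive post-baseline result.
- Report number and percentage by cohort and overall over the Immunogenicity Analysis Set, and optionally also over baseline-negative subjects.
- Show baseline-positive subjects on a separate line.
- State how a subject with no baseline result is handled.
- Keep the existing any-post-baseline line, labelled as post-baseline ADA prevalence.

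The cost is one SAP paragraph and two derived flags, for baseline status and developed ADA. The predose sample, the listing and the baseline rule already exist, so no new data are needed. A line for boosted subjects could be added from the titers, but only with a prespecified assay threshold, which the documents do not give.

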## **12. SOFTWARE**

SAS® Software Version 9.X. SAS Institute Inc., Cary, NC, USA.

## Appendix 1. Schedule of Assessments

### Study Procedures Table for Q2W/Q3W Dosing Schedule

	Screening	Treatment Phase (For Q2W and Q3W Dosing Schedules)								End-of-Treatment		Posttreatment Follow-up a			Survival Follow-up
		Cycle 1			Cycle 2			Every Subsequent Odd Cycle	Every Subsequent Even Cycle	End-of-Treatment Visit	30-Day Follow-up	Visit 1	Visit 2	Visits 3 and 4	
		1	2	8	1	2	8	1	1	At End-of-Treatment	30d from last dose	3m from last dose	6m from last dose	3m from last visit	3m from last visit
Visits Schedule (days)															
Schedule Window (days) b		+ 2		+ 2				+ 2 aa	+ 2 aa	≤ 7	± 7	± 7	± 7	± 7	
Administrative Procedures	< -28 days														
Informed consent	X														
Review of inclusion/exclusion criteria	X	X													
Issue Emergency Medical Support and Subject Card	X														
Review of medical history and demographics	X														
Review of baseline symptoms	X	X													
Review of prior and concomitant medications	X	X	X	X	X	X	X	X	X	X	X				
Cancer disease details and prior treatment	X														
Subsequent anticancer therapy status											X	X	X	X	
Clinical Procedures/Assessments	< -7 days														
Review AEs c	X	X	X	X	X	X	X	X	X	X	X				
Full Physical Examination	X										X				
Focused Physical Examination		X d		X				X	X		X	X	X	X	
Vital Signs, Weight and Height e	X	X	X	X	X	X	X	X	X	X	X	X	X	X	
12-lead ECG f	X	X f	X f	X f				X		X	X				
Echocardiogram or MUGA g	X g							X							
ECOG Performance Status d	X	X d	X	X	X	X	X	X	X	X	X	X	X	X	
Imaging Assessments h	< -28 days														
Tumor Imaging h	X	Every 6 weeks (± 7 days) the first 4 assessments then see footnote.													

	Screening	Treatment Phase (For Q2W and Q3W Dosing Schedules)								End-of-Treatment		Posttreatment Follow-up a			Survival Follow-up
		Cycle 1		Cycle 2		Every Subsequent Odd Cycle	Every Subsequent Even Cycle	End-of- Treatment Visit	30-Day Follow-up	Visit 1	Visit 2	Visits 3 and 4			
Visits Schedule (days)		1	2	8	1	2	8	1	1	At End-of-Treatment	30d from last dose	3m from last dose	6m from last dose	3m from last visit	3m from last visit
Schedule Window (days) b		+ 2		+ 2				+ 2 aa	+ 2 aa	≤ 7	± 7	± 7	± 7	± 7	± 7
Laboratory Procedures/Assessments i	< -28 days														
Blood for PK Assays j							X				X	X			
Blood for ADA Assays k						X					X	X			
CCI															
Blood for pharmacogenomics	X p														
CCI															
CCI															
Collection of required pretreatment biopsy (Phase 1b Cohort 2) z	X														
CCI															
Collection of required on-treatment biopsy (Phase 1b Cohort 2) y								X							
CCI															
Serum chemistry t	X	X d	X	X			X		X		X	X			
Hematology tests t	X	X d	X	X			X	X	X		X	X			
Coagulation tests t	X			X			X	X			X	X			
Endocrine function tests t	X			X			X	X			X	X			
Hepatitis Serology	X														
Urinalysis t	X			X	X		X	X			X	X			
Serum pregnancy test	X u														
Urine pregnancy test v,bb		X u						X			X	X	X bb		

	Screening	Treatment Phase (For Q2W and Q3W Dosing Schedules)								End-of-Treatment		Posttreatment Follow-up a			Survival Follow-up
		Cycle 1		Cycle 2		Every Subsequent Odd Cycle	Every Subsequent Even Cycle	End-of- Treatment Visit	30-Day Follow-up	Visit 1	Visit 2	Visits 3 and 4			
Visits Schedule (days)		1	2	8	1	2	8	1	1	At End-of-Treatment	30d from last dose	3m from last dose	6m from last dose	3m from last visit	3m from last visit
Schedule Window (days) b		+ 2		+ 2				+ 2 aa	+ 2 aa	≤ 7	± 7	± 7	± 7	± 7	± 7
HER2 Testing cc	X														
Study drug administration															
GS-1423 (All cohorts) w		X		X				X	X						
mFOLFOX6 (Phase 1b Cohort 1) x		X		X				X	X						
CCI															

5-FU = 5-fluorouracil; ADA = anti-drug antibody against GS-1423; AEs = adverse events; CRF = case report form; ECG = electrocardiogram; eCRF = electronic case report form; ECOG = Eastern Cooperative Oncology Group; HER2 = human epidermal growth factor receptor 2; IHC = immunohistochemistry; ISH = in situ hybridization; MUGA = multigated acquisition; PBMC = peripheral blood mononuclear cell; PD = progressive disease; PK = pharmacokinetics; Q2W = every 2 weeks; Q3W = every 3 weeks; SAE = serious adverse event

Note: Where applicable, assessments are to be performed prior to treatment unless otherwise indicated.

- a All subjects who discontinue treatment will have at least one 30-Day Follow-up Visit 30 days (± 7 days) from last treatment dose. Subjects who discontinue due to PD and/or start of a new line of therapy will then enter the Survival Follow-up Period for up to 12 months for survival status. Subjects who have discontinued treatment due to reasons other than PD and/or start of a new line of therapy will be in Posttreatment Follow-up for up to approximately 12 months from last treatment dose or until PD and/or start of a new line of therapy. Every effort should be made to collect subject information on the start of new anticancer therapy, PD, and death.
- b Treatment administration and associated procedures for that visit may be delayed for treatment-related AEs beyond the window and subsequent schedule adjusted accordingly.
- c After informed consent, but prior to initiation of study medication, the following types of events should be reported on the case report form (CRF/eCRF): all SAEs and AEs related to protocol-mandated procedures.
- d 72-hour window for C1D1 physical examination, safety labs, and ECOG performance status collection.
- e Vital signs will only be measured while subject is in seated or semi-recumbent position. Height only collected at screening. Phase 1a and Phase 1b (Cohort 2): Vital signs are to be measured prior to each infusion commencing, at the end of each infusion, and for the first 2 cycles, 1 hour (± 15 minutes) after the end of the GS-1423 infusion. Thereafter, the final vital signs can be taken 30 minutes (-10/+20 minutes) after the end of each GS-1423 infusion. Subjects will remain in the clinic under close supervision for the duration of this monitoring period. Phase 1b (Cohort 1): Additional vital signs for subjects being administered the mFOLFOX6 regimen will be measured as per standard institutional guidelines.
- f 12-lead ECG on Cycle 1 Day 1, before and 2 hours (-10/+20 minutes) after GS-1423 administration; on subsequent cycles, 12-lead ECG will be collected every odd cycle, on Day 1, at end of GS-1423 infusion(-10/+20 minutes), or as indicated. For subjects in Cohorts 5 through 8 and Cohort 10, a triplicate ECG will be performed at Cycle 1, Day 1 predose, at end of infusion, at 24 hours postdose (Day 2), and 168 hours postdose (Day 8).
- g Complete echocardiogram assessment will be conducted at screening to determine baseline (may be done within 14 days prior to the first dose of study treatment); and at every odd cycle, on Day 1, starting at Cycle 3 (±3 days). A MUGA scan is allowed.

- h The initial tumor imaging will be performed within 28 days prior to first dose. Scans performed as part of routine clinical management are acceptable for use as screening scan if they are of diagnostic quality and < -28 days prior to first dose. On-study imaging will be performed at 6, 12, 18, and 24 weeks ( $\pm$  7 days) from first treatment dose and then every 12 weeks thereafter. Imaging assessments will continue until PD as assessed by the investigator, unexpected toxicity occurs, or a new line of therapy is initiated for up to 1 year (Phase 1a and Phase 1b Cohort 2) or 2 years (Phase 1b Cohort 1). The timing of on-study treatment imaging should follow calendar days and should not be adjusted for delays in treatment administration or for visits. The same imaging technique should be used in a subject throughout the study. In general, lesions detected at baseline should be followed using the same imaging methodology and preferably the same imaging equipment at subsequent tumor evaluation visits.
- i Unless otherwise specified, samples should be collected before treatment administration. Refer to the Laboratory Manual for instructions and additional information.
- j PK Assays: Refer to Section 6; Table 6-3, Table 6-4, Table 6-5 and Table 6-6 in the body of the protocol.
- k ADA Assays: Refer to Section 6; Table 6-9 and Table 6-10 in the body of the protocol.
- l Not applicable (This footnote is obsolete with Amendment 1.)
- m Not applicable (This footnote is obsolete with Amendment 1.)
- n Not applicable (This footnote is obsolete with Amendment 1.)

p Blood pharmacogenomics sample collected from enrolled subject before or at C1D1, predose. If the sample is missed, it can be taken later on in the study.

- t Laboratory tests for screening should be performed within 28 days prior to the first dose of study treatment. After Cycle 1, predose laboratory procedures can be conducted up to 72 hours prior to dosing.
- u Serum  $\beta$ -human chorionic gonadotropin ( $\beta$ -HCG) pregnancy test for women of childbearing potential at screening within 72 hours of first treatment dose (if performed earlier in screening period, then a urine pregnancy test may be performed prior to first dose); urine pregnancy test at all other indicated visits; results must be available prior to dosing.
- v Urine pregnancy results to be obtained on site.
- w GS-1423 should be administered intravenously within 60 minutes (-10/+20 minutes). Subjects must be observed for 1 hour postinfusion for infusion-related reaction for the first 2 cycles and thereafter, 30 minutes after the end of the GS-1423 infusion. If administration of GS-1423 is delayed due to an AE, treatment visits may be delayed beyond the window of 3 days and schedules for subsequent visits should be adjusted accordingly.
- x The mFOLFOX6 regimen consists of leucovorin  $200 \text{ mg/m}^2$  and oxaliplatin  $85 \text{ mg/m}^2$  followed by bolus 5-FU  $400 \text{ mg/m}^2$  and a 46-hour infusion of 5-FU  $2400 \text{ mg/m}^2$ . Administration of mFOLFOX6 will immediately follow administration of GS-1423 on Day 1 of each cycle. The chemotherapy regimen mFOLFOX6 will be administered Q2W for up to 12 cycles (6 months). After 12 cycles, subjects may continue to receive 5-FU and leucovorin at the investigator's discretion until the subject meets study treatment discontinuation criteria.
- y Required on-treatment biopsy should be collected at C3D1 or up to 1 week prior on Q2W treatment cycle.
- z Required pretreatment biopsy must be obtained prior to C1D1 on a tumor from which 2 biopsies can be obtained (1 pretreatment and 1 on treatment).
- aa Treatment Phase visit window starting at Cycle 4 until End of Treatment is  $\pm$  2 days.
- bb This will only be performed for subjects receiving mFOLFOX6. Urine pregnancy tests will be performed at 4 months and 6 months after the last dose of mFOLFOX6.
- cc For subjects in Phase 1b Cohort 1 (gastric cohort) tumor tissue will be tested for HER2 status, if unknown, with an approved IHC and ISH kit.

CCI

